- g. Exercise-related adverse events will be collected from baseline/screening through the End of Study visit for all subjects. All other adverse events will be collected from the start of study drug. Serious adverse events are recorded from the time the informed consent form is signed until the Safety Follow-Up visit (or screen failure). In the event of no Safety Follow-Up visit, adverse event information will be collected through 30 days after the last dose of study drug. Subjects should be contacted by phone for adverse event follow-up if they do not come to the clinic for the Safety Follow-Up visit.
- h. Clinical laboratory tests may be performed at unscheduled visits if clinically indicated.
- i. Labs performed as part of screening are good for 30 days before randomization and do not need to be repeated.
- j. PSA may be performed at Unscheduled Visits as indicated to confirm PSA progression. No subject should discontinue study drug due to PSA rise during the first 12 weeks of therapy. Subjects with PSA progression on or after Week 17 must have progression confirmed by a second consecutive assessment conducted at least 3 weeks later before study drug discontinuation.
- k. CT of the abdomen and pelvis and bone scans should be performed to document that there is no definite evidence of metastatic disease at the time of screening. MRI of the abdomen and pelvis may be used in place of the CT.
- l. Baseline imaging performed per NCCN Guidelines⁸⁶ prior to informed consent as standard of care may be used so long as it is performed within 84 days prior to randomization.
- m. ADT (GnRH analogue) will be administered as per standard of care to maintain a castrate level of serum testosterone (<50 ng/dL) from Day 29 to Day 252.
- n. Muscular Strength and Muscular Endurance must be done at least 24 hours before or after CPET to allow adequate recovery time.
- o. Both the usual care group and the exercise training group will have a 4 week lead-in before starting ADT plus enzalutamide; only the exercise training group will undergo exercise training during this time.
- p. Day 1 is defined as the randomization day for Arm A (non-exercise) and the start of exercise for Arm B.
- q. Randomization may be done on Day 1 prior to the patient's exercise training session(s) for that week.
- r. DEXA scan for body composition should be fasting, if possible.

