9.11 Early Withdrawal of Subject(s)

9.11.1 Criteria for Early Withdrawal

Subjects may voluntarily withdraw from the study at any time. The PI may also withdraw a subject from the study at any time based on his/her discretion. Reasons for PI-initiated withdrawal may include, but is not limited to the following:

- Adverse events
- Abnormal laboratory values
- Abnormal test procedure results
- Protocol deviation
- Administrative issues
- Disease progression, defined as follows:
 - o PSA progression. PSA is evaluated per the Schedule of Events in Section 9. If a measured PSA is higher than the preceding value, then the rising PSA will be confirmed in 4 weeks (\pm 1 week) in the same laboratory as the first two values. If that third PSA value is higher still and the range of values is 50% above the baseline, then the patient is off study treatment. If not, the patient will remain on study, and the PSA will once again be checked when the patient presents for his regularly scheduled clinic visit.
 - o Radiographic progression (in the opinion of the investigator)

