9.11.2 Follow-up Requirements for Early Withdrawal

The Premature Withdrawal visit will be the same as the Safety Follow-Up visit. As mentioned above, all subjects discontinuing study drug for any reason will have a Safety Follow-Up visit approximately 30 days after their last dose of study drug or prior to initiation of cytotoxic or investigational therapy, whichever occurs first.

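### The early-withdrawal section lacks the 12-week bar on PSA-driven stopping that the Schedule of Events imposes, so a confirmed rise before the week-17 primary endpoint gets opposite instructions

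*Combined protocol and SAP*

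**What the plan says.** Two places in the protocol govern stopping for PSA.

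- **Section 9, Schedule of Events, footnote j** (attached to the PSA row): "No subject should discontinue study drug due to PSA rise during the first 12 weeks of therapy". For later rises it adds: "Subjects with PSA progression on or after Week 17 must have progression confirmed by a second consecutive assessment conducted at least 3 weeks later". It states no size of rise.
- **Section 9.11.1**, in the list of withdrawal reasons, under disease progression: "If a measured PSA is higher than the preceding value, then the rising PSA will be confirmed in 4 weeks", with a tolerance of one week either way. Then: "If that third PSA value is higher still and the range of values is 50% above the baseline", he is taken off study treatment. It gives no earliest date. The list opens with permissive wording: "Reasons for PI-initiated withdrawal may include, but is not limited to the following".

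Three other places bear on the point. Section 6.1.3 refers to men who have progressed yet are eligible to stay on study treatment, and gives no criterion for this. Section 9.11.2 says: "The Premature Withdrawal visit will be the same as the Safety Follow-Up visit". The schedule's end-of-treatment and safety column lists no CPET, and under Section 9.10 a man is off study once that visit is done. Sections 12.4.2 and 12.4.3 restrict the primary analysis to men with VO₂peak at both baseline and week 17.

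**The concern.** A site that reads only Section 9.11.1 would take a man off treatment in circumstances where a site that reads only footnote j must keep him on. The interval in which they disagree is the on-therapy period that leads up to the primary endpoint. The trial is open label at two centres, so the choice of passage could vary by site, or be made with knowledge of the arm.

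Two things are at stake. One is consistent exposure to enzalutamide plus ADT at Day 113, the background on which exercise is being tested. The other is whether the outcome is observed at all. The visit that follows early withdrawal has no CPET, and nothing says that a man off drug should still attend the Day 113 test.

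**Working it through.** **1. When the bar applies.** Therapy starts on Day 29 (Section 9). Twelve weeks are 12 × 7 = 84 days, and 29 + 84 = Day 113. That is the week-17 visit, so footnote j covers the whole on-therapy period before the nominal primary endpoint visit.

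**2. When Section 9.11.1 can trigger.** Four weeks ± 1 is 21 to 35 days.

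- Rise from Day 29 to Day 57: recheck on Day 57 + 21 = 78 to Day 57 + 35 = 92.
- Allowing the ±7-day window on Day 57: Day 50 + 21 = 71 to Day 64 + 35 = 99.
- Rise already present at Day 29: recheck on Day 50 to 64.

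The week-17 window is Day 113 ± 7, or Day 106 to 120. Every recheck date above falls before it opens. If the third value is higher still and meets the 50% condition, the man is off treatment under 9.11.1 and may not be stopped for that reason under footnote j.

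**3. Is the confirmation interval also in conflict?** Section 9.11.1 allows 3 to 5 weeks. Footnote j asks for at least 3 weeks. Any recheck timed by 9.11.1 satisfies footnote j, so these are compatible.

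**4. Is the size of rise in conflict?** Footnote j uses the term PSA progression without defining it, and 9.11.1 offers a definition. The two can be read together. The definition is itself unclear. PSA is scheduled at both Screening and Baseline Exercise Testing, so the baseline value is not identified, and the range of values is not explained. At the entry minimum of 0.01 ng/ml, 50% above baseline is 0.01 × 1.5 = 0.015 ng/ml.

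**5. Can the outcome be lost?** Sections 9.10 and 9.11.2 put the safety visit about 30 days after the last dose.

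- Stop on Day 78 to 92: visit near Day 108 to 122, which mostly overlaps the week-17 window.
- Stop on Day 50 to 64: visit near Day 80 to 94, before the window.

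In either case no CPET is listed at that visit and the man is off study after it. The interpolation in Section 12.4.3 needs a VO₂peak measured after week 17, but the schedule has no CPET beyond Day 113. The last-value-carried-forward sensitivity analysis could only use an earlier test, such as the one at Day 29.

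**6. Size.** Section 12.6 gives 20 evaluable men per arm, effect size d = 0.68, one-sided α = 0.10 and 80% power. For a two-sample t-test, df = n₁ + n₂ − 2, the noncentrality is d / √(1/n₁ + 1/n₂), and power is the probability that the noncentral t exceeds the 90th percentile of the central t.

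- 20 and 20: 0.68 / √0.1000 = 2.150; power 80.1%. This reproduces the plan's 80%.
- 19 and 20: 0.68 / √0.1026 = 2.123; power 79.3%.
- 17 and 20: 0.68 / √0.1088 = 2.061; power 77.5%.

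The last line is a pessimistic case. Section 6.3 cites a 92.5% rate of at least 80% PSA decline on enzalutamide monotherapy. If that rate applied here, 7.5% × 40 = 3 men would not reach an 80% decline. Failing to fall by 80% is far from rising by 50%, so three men is a loose upper guide.

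**The case against.** The best defence is that the two passages form one rule. The list in 9.11.1 is permissive and left to the investigator's discretion. Its PSA item points to the Schedule of Events, where footnote j sits on the PSA row. On this reading 9.11.1 says what progression is, and footnote j says when it may lead to stopping.

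Part of this stands. It disposes of any supposed conflict over the size of rise, and the intervals agree in any case. It does not remove the conflict over the 12 weeks. The pointer to the schedule concerns when PSA is measured; it does not import the bar or say which passage prevails. The permissive words introduce the list, whereas the PSA item states the consequence flatly.

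It is also fair to say that losing the primary outcome is not inevitable. A reader might infer that a man stopped for PSA automatically leaves the analysis. The documents do not say so. Section 9.11.1 takes him off study treatment, no passage cancels his Day 113 CPET, and in the Day 57 example the safety visit falls around the week-17 window. However, no passage asks for the test after stopping either, and 9.11.1 goes on to contrast being off treatment with remaining on study, which blurs the two. The absence of a CPET at the withdrawal visit affects withdrawal for any cause. The PSA wording is one route to it.

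**Conclusion.** The contradiction is real but narrow: one passage carries a 12-week bar on PSA-driven stopping, the other omits it, and the disagreement falls before the primary endpoint. A reader might infer that the rules also conflict on confirmation interval and on size of rise. The documents do not support that, although the baseline and the range of values need defining.

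The expected numerical effect is negligible: one man lost moves power from 80.1% to 79.3%, and even three from one arm leaves 77.5%. This rests on the planning assumptions of Section 12.6 and on PSA responses at least roughly like the cited monotherapy study, which included men with metastatic disease and did not test the combination. A case that the trial's power is threatened cannot be made from these documents. The reasons to act are that sites hold opposite instructions on stopping treatment, and that a man stopped early may go unmeasured in a complete-case analysis.

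**What to change.** - Reconcile footnote j, Section 9.11.1 and the remark in Section 6.1.3 about men continuing after progression into one rule, stated once and cross-referenced from the other places. It should give the time from which it applies, the confirmation interval, the size of rise, which PSA value is the baseline, and what the range of values means. Which rule applies is for the sponsor to decide; none is proposed here.
- State that men who stop study treatment before Day 113, for PSA or any other reason, are still asked to complete the Day 113 CPET, and distinguish stopping treatment from leaving the study.

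The cost is protocol wording. The Day 113 CPET is already scheduled for every man, so no new type of assessment is added.

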9.11.2 Follow-up Requirements for Early Withdrawal

The Premature Withdrawal visit will be the same as the Safety Follow-Up visit. As mentioned above, all subjects discontinuing study drug for any reason will have a Safety Follow-Up visit approximately 30 days after their last dose of study drug or prior to initiation of cytotoxic or investigational therapy, whichever occurs first.

9.11.3 Replacement of Early Withdrawal(s)

Subjects who withdraw prior to completing the baseline assessment for the primary endpoint will be replaced. See also Sections 9.1 and 9.2 for eligibility criteria, as well as 12.1 and 12.4.3 for analysis related to withdrawals.

9.12 Study Assessments

9.12.1 Medical History

Medical history, such as previous treatments, procedures, and conditions will be collected during the screening period.

9.12.2 Physical Exam

Evaluations should be performed by the same evaluator throughout the study whenever possible. Weight will be recorded at every visit. Height will be recorded at screening visit only. Body mass index (BMI) will be calculated at every visit. Vital signs include upright blood pressure, heart rate, respiratory rate, and oral or aural body temperature. A complete physical examination is required at the Screening, Day 113, and Day 252 visits. A brief symptom-directed physical examination should be performed at all other clinic visits.

9.12.3 Correlative Assessments

All Correlative Assessments will be performed at Day 1 and Day 113 (see Schedule of Events at the beginning of this Section for details). Patient reported outcomes will also be performed at Day 252. In addition, a CPET will be performed at Day 29 to assess VO₂peak changes during the Lead-In Period and Metabolomics samples will be drawn at Day 57 to assess for early changes that may predict later changes in metabolic parameters. All samples will be collected in the fasting, pre-exercise state unless otherwise noted below.

Cardiopulmonary Exercise Testing (CPET)

Exercise Capacity will be assessed using a symptom-limited CPET on a motorized treadmill with expired gas analysis to determine VO₂peak, according to guidelines for clinical populations.⁹⁰ All CPET data will be recorded as the highest 30s value elicited during the CPET. During exercise, heart rate and rhythm will be monitored continuously using a 12-lead ECG. Equipment with similar technical specifications will be used across the two study sites to ensure reasonably accurate and precise results.

Physical Functioning / Functional Capacity

Physical Functioning / Functional Capacity will be assessed using the following assessments: chair-stand test, timed up and go, and 6 min walk distance outcomes as described previously.^{91 57,92,93} These measures will complement the exercise capacity measure.

Chair-Stand Test: The 5-repetition chair-stand test measured the time taken to complete 5 repetitions of the sit-to-stand maneuver. All sit-to-stand maneuvers will be performed from a chair without an arm rest at 43cm in height and 47.5cm in depth. Standardized instructions will be provided as follows: "By the count of 3, please stand up and sit down as quickly as possible for

5 times. Place your hands on your lap and do not use them throughout the procedure. Lean your back against the chair's backrest at the end of every repetition." Timing will start when the subject's back left the backrest and will be stopped once the back touched the backrest.

Timed Get Up and Go: Subjects will be required to stand up from a chair with armrests, walk 3m, turn around, return to the chair, and sit down. The time taken to complete this task will be measured in seconds with a stopwatch.⁹³

6-minute Walk Distance (Duke patients only): The six minute walk test will be conducted according to the guidelines of the ATS.⁹⁴ Subjects will be instructed to cover the longest distance possible in six minutes under the supervision of an exercise physiologist or trained designee. The distance walked will be determined in a measured corridor, between 2 cones that were placed 30 meters apart. The test will be performed twice at each study timepoint with the average recorded. Age and sex-predicted 6MWD will be calculated from the equation of Gibbons et al.⁹⁵

Quantitative Skeletal Muscle Function

Quantitative Skeletal Muscle Function will be assessed by two outcomes:

Muscle Cross Sectional Area (CSA; protocol v1-v15 only) of the dominant thigh will be assessed using magnetic resonance imaging (MRI) with a 3.0T-scanner (Siemens Tim Trio 3 Tesla MRI, Erlangen, Germany). Imaging will be performed using sequence turbo spin echo (T1-weighted sequence) recall scans at the mid-femur level. Seventeen serial slices will be obtained with one at the juncture of the middle third of the femur (this point will be landmarked to ensure within subject reproducibility) as previously described.⁹⁶ The CSA of the quadriceps, hamstrings, and total mid-thigh muscle will be assessed using semiautomatic generation of the region of interest using a combination of console software and/or third party commercially available independent workstation in conjunction, as needed. If the patients MRI screening form is positive, the muscle CSA will not be performed but the subject will continue on the study.

Muscular Strength of the upper and lower body will be assessed as a *one-repetition maximum* (1-RM). This dynamic strength assessment will be conducted using the following exercises: leg press, chest press, and row. The heaviest weight lifted while adhering to the strict technique and form will be used to score the assessment. A certified exercise physiologist or trained designee will conduct this assessment in a controlled environment. A 1-RM is defined as the greatest resistance that can be moved through the full range of motion in a controlled manner. Mean percentage of age and sex-predicted muscle strength will be obtained from available normative data.

Muscular Endurance of the upper and lower body will be assessed as the *number of repetitions to fatigue at 70% of the 1-RM*. The same exercises and methods will be used as in the 1-RM determination, detailed above. Subjects will continue until technique, tempo, volition or inability to complete two consecutive repetitions causes finality (per discretion of the exercise physiologist or trained designee).

Metabolic Control (protocol v1-v15 only)

Subjects will undergo sampling of fasting, pre-exercise, **plasma insulin** and **glucose** concentrations for calculation of **HOMA-IR**, as previously described.⁹⁷ **Glycosylated hemoglobin** (HgbA1c) will also be measured. These will be measured in a CLIA-certified clinical laboratory.

Body Composition

Body composition will be assessed by dual energy x-ray absorptiometry scan in the morning (after an overnight fast, if possible). Transverse scans from head to toe measured absorption of x-ray beams at two different energy levels allowing for a valid determination of lean body mass, fat mass and fat percentage.

Patient Reported Outcomes

Data on health related quality of life will be collected using the Functional Assessment of Cancer Therapy-Prostate (**FACT-P**) scale, which can be found in **Appendix C**.^{98,99} Data on subject-reported changes in fatigue will be collected using the Functional Assessment in Chronic Illness Therapy – Fatigue questionnaire (**FACIT-F**), which can be found in **Appendix B**. Data on leisure time exercise habits will be collected using the 4-item **Godin Leisure Time Exercise Questionnaire**, which can be found in **Appendix D**.¹⁰⁰

Food Frequency Questionnaire (FFQ)

A food frequency questionnaire (FFQ) developed by the Nutrition Assessment Shared Resource (NASR) of Fred Hutchinson Cancer Research Center (FHCRC) will be administered at the Week 1 and Week 17 time points to explore the collinearity of diet/exercise and to potentially correct for imbalances in the dietary intake between arms. Participants will be queried regarding their dietary intake over the last 1 month prior to completing the questionnaire.

Specifically, nutrient data will be collected using the Men's Nutritional Assessment (MNA). Nutrition Assessment uses the University of Minnesota Nutrition Data Systems for Research (NDSR) software for data entry and nutrient analysis via the FFQ. A sample booklet is provided at:

<http://sharedresources.fhcrc.org/sites/default/files/FFQ-MNA-Sample.pdf>

Questionnaires will be batched (approximately 30-40 questionnaires/batch) and sent via UPS/FedEx to NASR for scanning. FFQs are optically scanned at FHCRC. Each batch of scanned FFQs yields files containing food consumption data, nutrient intake data, and an error report that specifies questionnaire completion errors (e.g. incomplete erasures, missed questions).

Following is the contact information for the NASR:

Location: [name]
Mailing Address: [name]
Phone: [REDACTED]
Fax: [REDACTED]
Email: [REDACTED]
Contact: [name], M.S.,R.D.,C.D., Director

Prostate-Specific Antigen (PSA)

Prostate-Specific Antigen (PSA) will be measured in a CLIA-certified clinical laboratory.

Metabolomics

Fasting EDTA plasma will be collected from each participant at each time point and stored at -80°C for metabolic profiling. Refer to lab manual for blood collection volumes. Metabolic intermediates will be measured using a targeted, mass spectrometry (MS)-based platform as described previously.¹⁰¹ Profiling will include ~96 serum metabolic intermediates, hormones of energy regulation, and serum cytokines known to be associated with insulin sensitivity, exercise/diet induced changes, or treatment with ADT (**Table 2**). Our collaborators at the Stedman Center at Duke have reported sample preparation methodology and coefficients of variation for each assay.^{102,103} Cytokines and inflammatory markers will be measured using a Luminex panel. Conventional metabolites will be measured in a CLIA-certified clinical laboratory.

Table 2. Targeted Metabolomics Analysis – Metabolic Factors to be Assessed

Conventional Metabolites	C-reactive protein (CRP), glucose, total cholesterol, HDL, LDH, triglycerides, total free fatty acids, ketones, 2-OH butyrate, 3-OH butyrate, succinate, steroids (multiple ³⁵)
Energy Hormones	Insulin, ghrelin, adiponectin, leptin, glucagon, C-peptide, IGF-1, IGFBP-1, -2, -3, resistin

Cytokines	TNF- α , IL-1 β , IL-2, IL-6, IL-8, IL-10, IL-12p40, IL-12p70, IFN- γ
Amino Acids^{102,104,105}	Glycine, alanine, serine, proline, valine, leucine/isoleucine, methionine, histidine, phenylalanine, tyrosine, Asx (asparagine, aspartate, aspartic acid), Glx (glutamate/glutamine/glutamic acid), ornithine, citrulline, arginine
Acylcarnitines (AC)/Other¹⁰⁶	~30 selected AC, including C3, C5; medium and long chains; cholate; dicarboxylic acids

All metabolomics samples will be prepared as specified in the SOP document, "Preparing samples for submission to the Metabolomics Laboratory, Sarah W. Stedman Nutrition & Metabolism Center, Duke University Medical Center." Samples will be batched and sent to the Duke Biospecimen Repository and Processing Core (BRPC) for storage for future analysis via courier or FedEx/UPS at the following address:

Duke Biospecimen Repository and Processing Core
[name]
[name]

Prior to shipping, the BRPC must be contacted either by phone or email to confirm that someone will be available to receive the shipment on the desired delivery date. Written or verbal confirmation must be obtained from the BRPC staff prior to the shipment.

10 SAFETY MONITORING AND REPORTING

The PI is responsible for the identification and documentation of adverse events and serious adverse events, as defined below. At each study visit, the PI or designee must assess, through non-suggestive inquiries of the subject or evaluation of study assessments, whether an AE or SAE has occurred.

